7.2.8 Unscheduled visits

To document breakthrough infections, enrolled participants will be requested to contact the Study Team if they develop symptoms of COVID-19. They will all be asked to take a RAT test and, if they test positive, may be asked to take a second nasal swab. The second swab will be stored for sequencing. To enrol those with severe disease and those with higher viral load, the second swab will be requested for the first 5-10 cases per month who present within three days of symptom onset, plus any severe cases. A representative sample of positive nasal swabs will be chosen for whole genome sequencing following

the completion of the 12 month visit and at the end of the study. All positive RAT tests and details regarding symptoms will be documented for all participants.

An optional blood sample (10ml, i.e., 5ml sodium heparin + 5 ml SST tube) will be collected if the participant consents 28 days after a positive RAT test (convalescent blood). The convalescent blood sample will determine whether breakthrough infections boost SARS-CoV-2 specific immune responses in previously vaccinated or control group individuals by comparing them to immune responses from previous blood samples. CMI will also be accessed. We will explore the association between immune protection and viral variants and identify potential viral signatures associated with severe breakthrough infections and/or immune escape. The participant will otherwise continue with scheduled study visits. The study team will maintain telephone contact with all participants who test positive for the course of their illness and fully document all telephone calls. With the participant's permission, the study team will seek clinical data from the health care providers or hospital(s) if the subject becomes clinically ill.

In-between study visits, participants will be sent 3 monthly SMS messages to remind them to report all breakthrough infections.

7.2.9 Withdrawal of consent - participant withdraws from all trial participation

A participant has the right to withdraw from the trial at any time and for any reason and is not obliged to give his or her reasons for doing so. The Investigator may withdraw the participant at any time in the interests of the participant's health and well-being. In addition, the participant may withdraw/be withdrawn for any of the following reasons:

- Administrative decision by the Investigator
- Ineligibility (either arising during the trial or retrospectively, having been overlooked at screening).
- Significant protocol deviation
- Participant non-compliance with study requirements

The reason for withdrawal will be recorded in the eCRF. If the participant has an AE at the time of withdrawal, appropriate follow-up visits or medical care will be arranged, with the agreement of the participant, until the AE has resolved, stabilised, or a non-trial-related causality has been assigned.

If a participant withdraws from the study, storage of samples and data collected before their withdrawal will still be used in the analysis unless the participant specifically requests otherwise.

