5.2.6 Excluded medications and treatments

There are no excluded medications or treatments for enrolled participants.

Study participants will be asked to inform us of any non-study COVID-19 vaccine doses that they receive before their 30 month visit.

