5.2.8 Discontinuation from trial intervention

See Section 7.2.9.

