5 DESCRIPTIVE STATISTICS

5.1 PARTICIPANT DISPOSITION

A CONSORT flow diagram will be used to summarise the study population from screening to analysis, including the number of people who were:

- Screened for eligibility
 - and were eligible at screening
 - and were ineligible at screening (screen failures)*
- Eligible at screening but not randomised*
- Ineligible at screening but randomised (protocol violation)*
- Eligible and randomised (or not randomised for the control group)

[Subsequent numbers will be given by study group]

- Allocated to each study group
 - and received the allocated vaccine
 - and did not receive the allocated vaccine*
- Included in the Reactogenicity and Safety Population (according to vaccine received not allocated)[^]
- Included in the Primary Day-28 Immunology Population[^]
- Included in the Month-6 Immunology Population[^]
- Included in the Month-12 Immunology Population[^]

* Reasons will be provided.

[^]The number of participants with missing data will be noted. Missing data arising from lost-to-follow-up or withdrawal will be enumerated, including the level of withdrawal (from intervention, follow-up, or both, and consent to use data up to the time of withdrawal) and reasons (harms-related reasons for withdrawal will be emphasised).

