5.3 ADHERENCE AND PROTOCOL DEVIATIONS

Adherence to the intervention is defined as receiving a trial booster vaccination on Day 0. The number and percent of participants who adhered will be presented by study group.

Pre-defined major protocol deviations (with a direct bearing on the primary outcome) are:

- Inclusion and randomisation of an ineligible person
- Receiving the wrong trial vaccination
- Day-28 visit occurring outside of the specified time window (between Day 25 and 35 [inclusive], with Day 0 being the day of trial vaccination)

All protocol deviations will be classified as minor or major before unblinding. Major protocol deviations are those that are deemed to significantly affect the rights or safety of a trial participant, or the reliability, accuracy, and robustness of the data. The number and percentage of patients with major and minor protocol deviations will be summarised by study group (as per randomisation), with details of type of deviation provided.

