7.2 MAIN ANALYSIS OF THE PRIMARY ENDPOINTS

Table 6 and Table 7 are the Estimand-to-analysis tables for the primary immunological and reactogenicity endpoints, respectively.

Table 6. Estimand-to-Analysis table⁵ for immune response (binding antibodies- IgG) at Day-28 (primary immunogenicity endpoint)

Primary Objective (as per Protocol):	
Assess and compare the immune response in two randomised vaccine groups (bivalent Moderna and Novavax) at 28 days post-vaccination measured as binding antibodies (IgG ELISA – Wuhan) who have been boosted at least six months earlier.	
Estimand:	Geometric mean ratio (GMR) of binding antibodies (IgG ELISA – Wuhan) 28 days post-vaccination comparing the two vaccine groups (bivalent Moderna and Novavax) in adults 18 years or older who have received their third dose of COVID-19 vaccine at least six months previously, irrespective of SARS-CoV-2 infection.
ESTIMAND Attributes:	Incorporation of Estimand Attribute in ANALYSIS:
Treatment Bivalent mRNA Moderna COVID-19 vaccine and protein-based Novavax COVID-19 vaccine	Study arms Bivalent Moderna vaccine arm (Moderna BA.1 and Moderna BA.4-5 groups combined) Novavax vaccine arm
Target population Adults 18 years or older who have received their third dose of COVID-19 vaccine at least six months previously	Analysis set (“Primary Day-28 Immunology Population”) All randomised participants as per randomisation with complete outcome and covariate data
Variable Binding antibodies (IgG ELISA for Wuhan, Omicron BA.1 and Omicron BA.4/5) 28 days after trial vaccination	Outcome measure Geometric mean concentrations of binding antibodies at the Day-28 visit (25 – 35 days post-booster)
Handling of intercurrent events	Handling of missing data
Event (up to and including Day-28 visit)	Strategy⁴
SARS-CoV-2 infection	Treatment Policy [#] (interpret results in conjunction with breakthrough infection rates) If >5% of participants are excluded due to missing data, a supplementary analysis will be performed with multiple imputation.

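### Protocol 7.2.9 permits staff to end all follow-up of a randomised participant for ineligibility, deviation, non-compliance or administrative reasons, which can only create avoidable missing data in the as-randomised analysis

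*Protocol*

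**What the plan says.** Protocol 7.2.9 (the withdrawal section; the number is also used for the 24-month visit) covers leaving all trial participation. It gives the participant's own choice and a clause on the participant's health and well-being, and then continues: "In addition, the participant may withdraw/be withdrawn for any of the following reasons". The list that follows contains an administrative decision by the investigator, significant protocol deviation, "Participant non-compliance with study requirements" and "Ineligibility (either arising during the trial or retrospectively, having been overlooked at screening"). After withdrawal, the section provides for follow-up of an AE that is open at that time and for use of samples and data already collected. It provides for no further outcome collection. Protocol 7.2.11 bars replacement.

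Protocol 5.2.8, on discontinuing the intervention, consists of "See Section 7.2.9". Protocol 5.2.6 states: "There are no excluded medications or treatments for enrolled participants". Protocol 5.2.7 has immunosuppressive therapies recorded up to 30 months.

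On the analysis side, SAP Table 6 (section 7.2) defines the primary immunology set as "All randomised participants as per randomisation with complete outcome and covariate data". SAP 5.3 lists randomisation of an ineligible person and "Receiving the wrong trial vaccination" among the pre-defined major deviations, summarised by randomised group, with no exclusion stated. SAP 5.1 plans to enumerate missing data from withdrawal, "including the level of withdrawal (from intervention, follow-up, or both").

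**The concern.** Each vaccinated participant receives one dose at Visit 1. From then on there is no trial treatment left to stop, so a staff-initiated withdrawal can end only measurement. The four listed reasons come in addition to participant choice and the health and well-being clause, so they are neither consent nor safety reasons. Two of them, ineligibility and deviation, describe people whom the SAP intends to keep in their randomised group.

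At stake is selective loss after randomisation. Someone given the wrong vaccine, or found after vaccination to have had a confirmed infection within the three months before enrolment, may well have titres unlike the rest of the arm. The main analysis is complete-case, so a person withdrawn before a blood draw drops out of that comparison. SAEs that begin after withdrawal are also not captured, although the schedule of assessments documents SAEs throughout the study.

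**Working it through.** **1. The passages side by side.**

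| Topic | Protocol | SAP |
|---|---|---|
| Ineligible person randomised | 7.2.9: may be withdrawn from everything | 5.3: major deviation, counted by randomised group |
| Wrong vaccine given | 7.2.9: may be withdrawn as a significant deviation | 5.3: major deviation; Table 7 and 9.6 analyse reactogenicity and safety by vaccine received |
| Levels of withdrawal | One level only; 5.2.8 points to 7.2.9 | 5.1: intervention, follow-up, or both |
| Medication started after enrolment | 5.2.6: nothing excluded; 5.2.7: immunosuppressives recorded to 30 months | - |
| Outcomes after withdrawal | None; open AEs only | 6.5: missing data; main analysis complete-case |

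No section of either document keeps a participant withdrawn for these reasons in the blood draws.

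**2. Is power threatened?** Inputs from Protocol 11.1: CV 1.15, GMR 1.4, two-sided 0.05, 90% power, 160 per arm, about 20% loss.
- SD of ln titre = sqrt(ln(1 + 1.15²)) = 0.918.
- n per arm = 2 × (1.960 + 1.282)² × 0.918² / (ln 1.4)² = 157, against 160 stated. Power at 160 is 90.6%. 160/(1 - 0.20) = 200. The plan's figures reproduce.
- With 225 per arm, power is 97.3% with no loss and 93.5% at 20% loss. Evaluable numbers fall to 160 only at 1 - 160/225 = 28.9% loss.

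So the issue is bias, not power.

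**3. How large could the bias be at Day 28?** The documents give neither a withdrawal rate nor a titre difference, so both are assumptions. Suppose a share f of one arm only is withdrawn before Day 28 and its GMC differs r-fold from those retained. The shift in ln GMR is then f × ln r in absolute size. The unadjusted SE of ln GMR is 0.918 × sqrt(2/225) = 0.0865.

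| f | r | Shift in ln GMR | GMC factor | In SE |
|---|---|---|---|---|
| 2% | 2 | 0.0139 | 1.014 | 0.16 |
| 2% | 4 | 0.0277 | 1.028 | 0.32 |
| 5% | 2 | 0.0347 | 1.035 | 0.40 |
| 5% | 4 | 0.0693 | 1.072 | 0.80 |

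The shift is nil if r = 1, and it cancels if both arms lose the same share with the same r.

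**4. Would imputation be triggered?** The SAP threshold is more than 5% missing. Over the two arms that is 0.05 × 450 = 22.5 people. Losing 5% of one arm is 11.25 people, or 2.5% of 450, so these withdrawals alone would not reach it.

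**5. Later endpoints.** Data from before withdrawal are kept, so someone withdrawn after the Day-28 sample still counts for the primary endpoint. The clause then operates over the visits from Month 6 to Month 30, where the time at risk is far longer. With no rates given, that effect cannot be sized.

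**The case against.** The clause says may, not must. A reader might infer that outcomes will not be collected from these people, or that the as-randomised set becomes a per-protocol set in practice. The documents do not support that: nothing requires withdrawal for any listed reason, and the SAP plainly expects ineligible and wrongly vaccinated participants to be carried forward.

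A reader might also see a conflict with the treatment policy strategy. For the primary endpoint that strategy covers SARS-CoV-2 infection only; at later timepoints a self-initiated fifth dose is added. Ineligibility, deviation and non-compliance are not intercurrent events in this plan. The tension is with the as-randomised set, and even that set is limited to complete data.

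Two tempting illustrations fail. Someone who starts an immunosuppressant in month 10 might be called ineligible during the trial, but the exclusion is worded for current use at enrolment, and 5.2.6 and 5.2.7 show that such people are meant to be followed. Someone who does not return a paper diary card could hardly be removed before Day 28 on that ground: the card is collected at that visit, and its contents are obtained by phone or picture at Day 7.

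The SAP also has safeguards: missingness by arm and timepoint, baseline comparison of those with and without missing data, titre plots by time of withdrawal, reasons for withdrawal, and arm-specific imputation that conditions on baseline titre and covariates. No mechanism for imbalance between arms is shown, and laboratory staff stay blinded. Finally, the vaccinator randomises at the vaccination visit, so a separate off-intervention state will be rare.

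These points limit the size of the concern. They do not remove it: the safeguards describe or model missing data that need not arise, and no text tells staff to keep these participants in follow-up.

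**Conclusion.** The point stands as an avoidable weakness in the withdrawal rule. Protocol 7.2.9 permits withdrawals that stop outcome and new-SAE collection and nothing else, for reasons that the SAP treats as reportable deviations. It also leaves the protocol without the off-intervention, still-followed level that SAP 5.1 plans to report.

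The likely effect on the Day-28 GMR is small. The 0.16 to 0.80 SE range rests on assumed rates and titre differences, with every withdrawal in one arm and shifted in the same direction. Real cases may pull in opposite directions or be shared between arms. Exposure is greatest for the 6- to 30-month endpoints. The sample size is not in question. The change is worth making because it is cheap and prevents a loss that more participants would not cure.

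**What to change.** - **Protocol 7.2.9:** state that ineligibility, protocol deviation, non-compliance and administrative reasons are recorded as deviations and do not by themselves end follow-up. Such participants keep their scheduled blood samples, infection reporting and SAE contact unless they withdraw consent, their consent is found not to have been valid, or the existing health and well-being clause applies. The consent exception is needed: simply deleting ineligibility as a reason would also cover someone later found unable to give informed consent or to understand English.
- **Protocol 5.2.8:** state that not receiving the allocated vaccine, or receiving the wrong one, does not end follow-up.
- **eCRF:** record the level of withdrawal, as SAP 5.1 expects.

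Cost: protocol wording and one eCRF field, with no new procedures and no change in sample size. The downside is that a few participants with deviations stay on the existing visit schedule.

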7.2.10 Losses to follow-up

A participant will be considered lost to follow-up if he/she fails to return for two consecutive visits and is unable to be contacted by the trial staff. The following action must be taken if a participant fails to return to the clinic for a required trial visit:

- Trial staff will attempt to contact the participant within one week of the missed visit and reschedule the visit.

- Before a participant is deemed lost to follow-up, trial staff will make every effort to regain contact. Three telephone calls will be made, and two emails will be sent. All contact attempts will be documented in the participant's eCRF.
- If the participant continues to be unreachable, he/she will be considered to have withdrawn from the trial with a primary reason of loss to follow-up.

7.2.11 Replacements

Participants who have been randomised and enrolled may NOT be replaced.

7.2.12 Trial Closure

The end of the trial is the date of the last assay for primary and secondary outcomes conducted on the last sample collected.

8 SAFETY MONITORING AND REPORTING

8.1.1 Definitions for use in trials involving investigational medicinal products

Participant-specific adverse events

Adverse events must be assessed to determine each of the following:

1. Seriousness
2. Relatedness (i.e., causal relationship)
3. Expectedness

Adverse Event (AE): Any untoward medical occurrence in a patient or clinical trial participant administered a medicinal product and does not necessarily have a causal relationship with this treatment.

Adverse Reaction (AR): Any untoward and unintended response to an investigational medicinal product related to any dose administered.

Comment: All adverse events judged by the reporting investigator or the sponsor as having a reasonable possibility of a causal relationship to an investigational medicinal product would qualify as adverse reactions. The expression 'reasonable causal relationship' means to convey, in general, that there is evidence or argument to suggest a causal relationship.

Serious Adverse Event (SAE) / Serious Adverse Reaction (SAR): Any adverse event/adverse reaction that results in death, is life threatening, requires hospitalisation or prolongs existing hospitalisation, results in persistent or significant disability or incapacity or is a congenital anomaly or birth defect.

Note: Life-threatening refers to an event in which the participant was at risk of death at the time of the event. It does not refer to an event that hypothetically might have caused death if it were more severe. Medical and scientific judgement should be exercised in deciding whether an adverse event/reaction should be classified as serious in other situations. Important medical events that are not immediately life-threatening or do not result in death or hospitalisation but may jeopardise the participant or require intervention to prevent one of the other outcomes listed in this definition should also be considered serious.

Suspected Unexpected Serious Adverse Reaction (SUSAR): An adverse reaction that is both serious and unexpected.

Safety issues (requiring expedited reporting)

The following definitions describe additional safety events that require expedited reporting to stakeholders, including the Sponsor, Investigators, HREC, local governance office and TGA:

Significant Safety Issue (SSI): A safety issue that could adversely affect the safety of participants or materially impact the trial's continued ethical acceptability or conduct.

Comment: An SSI is a new safety issue or validated signal considered by the Sponsor in relation to the investigational medicinal product that requires urgent attention of stakeholders. This may be because of the seriousness and potential impact on the benefit-risk balance of the investigational medicinal product, which could prompt regulatory action and/or changes to the overall conduct of the clinical trial, including monitoring safety and/or the administration of the investigational medicinal product.

Urgent Safety Measure (USM): A measure required to eliminate an immediate hazard to a participant's health or safety. Note: This type of SSI can be instigated by either the investigator or sponsor and can be implemented before seeking approval from HRECs or institutions.

8.2 Capturing and eliciting adverse event/reaction information

Participants will be asked to record local and systemic AEs for 7 days (and longer if symptoms persist at day seven, until resolution or stabilisation) following vaccination in the electronic or paper diary card (solicited AEs). Unsolicited AEs - all local and systemic AEs occurring in the 28 days following vaccination observed by the Investigator or reported by the participant, whether attributed to study medication, will be recorded in the AE section of the eCRF.

Serious adverse events (SAEs) will be followed up for the duration of the trial. Adverse events of special interest will be categorised as per CEPI guidelines (17).

Any unexpected, serious, or unusual AE following immunisation will be reported to SAEFVIC (vaccine safety surveillance service) through SAFEVAC: Integrated Vaccine Safety website that automatically forwards reports to the TGA (<https://www.safevac.org.au/Home/Info/VIC>). Adults who experience a significant adverse event reported to SAEFVIC (<https://mvec.mcri.edu.au/saefvic/>) should be referred to the Victorian Specialist Immunisation Services (VicSIS) for review and management of future COVID-19 vaccination.

8.3 Documentation of AEs

The AE will be described in the source documents (e.g., electronic or paper diary card) and captured on the eCRF and will include:

- A description of the AE
- The onset date, duration, date of resolution
- Severity (mild, moderate, or severe – how does the event impact the participant's daily life?)
- Seriousness (i.e., is it an SAE?)

- Any action taken (e.g., treatment, follow-up tests)
- The outcome (recovery, death, continuing, worsening)
- The likelihood of the relationship of the AE to the trial treatment (Unrelated, Possible, Probable, Definite)

Changes in the severity of an AE will be reported. AEs characterised as intermittent will be documented for each episode. All AEs will be followed to adequate resolution, where possible.

8.4 Assessing the relatedness (causality) of a participant's AE

The relationship of the event to the trial intervention will be graded/ assessed as follows:

Unrelated	Unlikely temporal relationship to study product. Alternate aetiology likely (clinical state, environmental or other interventions) and does not follow known typical or plausible pattern of response to study product
Possible	Reasonable temporal relationship to study product; or event not readily produced by clinical state, environmental or other interventions; or similar pattern of response to that seen with other vaccines
Probable	Reasonable temporal relationship to study product; and event not readily produced by clinical state, environment, or other interventions or known pattern of response seen with other vaccines
Definite	Reasonable temporal relationship to study product; and event not readily produced by clinical state, environment, or other interventions; and known pattern of response seen with other vaccines

